Fred Hutchinson Cancer Research Center University of Washington Seattle Cancer Care Alliance

Decitabine plus cytarabine for Induction of Remission in Newly Diagnosed Elderly Acute Myeloid Leukemia (AML) and Advanced Myelodysplastic Syndrome (MDS)

Current Version: 10.03.16 Previous Version: 07.31.15

Principal Investigator: [name], PhD

Professor of Medicine, UW Associate Member, FHCRC University of Washington [name]

[name]

Email: [contact]

Sub-Investigators:

[name]

Professor of Medicine, UW

Member FHCRC

[name]

[contact]

Email: [contact]

[name]

Assistant Member, Biostatistics and Biomathematics Program, PHS Fred Hutchinson Cancer Research Center

[contact]

Email: [contact]

Seattle Cancer Care Alliance Network Investigators

Sub Investigators			
[name]	Bozeman Deaconess Cancer Center [contact]; [contact] [contact] for after hours calls		
[name]	Columbia Basin Hematology and Oncology [contact]		
[name]	Evergreen Hospital Medical Center [contact] [contact] for after hours calls		
[name]	Group Health Cooperative Bellevue clinic: [contact]; Bellevue Urgent Care: [contact]; Seattle clinic: [contact]; Seattle Urgent Care [contact] or [contact] for paging operator after hours		
[name]	MultiCare Health System [contact] [contact]		
[name]	Olympic Medical Center [contact]		
[name]	Skagit Valley Hospital [contact]		
[name]	Wenatchee Valley Medical Center [contact]		

Table of Contents

1.	Study Objective	4
2.	Rationale	4
3.	Patient Eligibility	6
4.	Pre-Treatment Evaluation	7
5.	Treatment Plan	7
6.	Post Treatment Testing	8
7.	Criteria for Removal from Study	8
8.	Statistical Considerations	8
	a. Statistical objective	8
	b. Study design	9
9.	Stopping Rules	9
10.	Regulatory Reporting Requirements	1
	a. Adverse Event reporting1	1
	b. Grade 3-4 toxicity expectations	2
11.	Data and Safety Monitoring Plan	2
12.	Data Management/Confidentiality	2
13.	References	3
14.	Appendix: Treatment-Related Mortality (TRM) Score18	

1. Objectives

- a.) Examine whether a combination of decitabine given for 10 days (days 1-10), rather than the usual 5 days, plus "standard dose ara-C (100 mg/m2 daily days 1-7) might improve 6-month survival probability from the historical 65% to 80% in patients age \geq 60 with newly diagnosed AML
- b.) Test whether this combination might maintain CR rate at our historic 45% in these patients
- c.) Study factors that lead physicians to escalate or maintain ara-C doses in those patients who have had an "intermediate response" short of CR to the first 2 cycles of the combination
- d.) While maintaining awareness of confounding covariates, examine the effect of such dose escalation on CR rate

2. Rationale

It is generally recognized that most patients age ≥ 60 with newly-diagnosed AML live less than 9-12 months with therapies such as 3 days of daunorubicin (or idarubicin) and 7 of ara-C ("3+7"), low-dose ara-C (LDAC) and, more recently, azacitdine or decitabine (1,2). The principal cause of death is not treatment-related mortality, rates of which appear to be declining sharply even after 3+7 (3). Rather failure is generally due to "resistance", i.e. failure to enter CR despite living long enough to do so or relapse from CR (4, 5). Principal covariates associated with resistance are cytogenetics (1) (for failure to enter CR), and, for relapse, cytogenetics, slow count recovery(6), molecular markers (aberrations in NPM, CEBPA, ASXL, DNMT3a) (7),type of response (CR vs. CRp or CRi) (8), and minimal residual disease at CR (9).

Given their poor predicted outcome with standard therapy, older patients are typically candidates for "clinical trials" (1). However a search of the NCI website clinicaltrials.gov indicates > 50 trials for older patients with newly-diagnosed AML. This can only indicate that pre-clinical rationales are insufficient to indicate which trial is best. The failure of most new agents to substantially improve outcome despite their seemingly compelling rationales lends further support to this supposition. Thus empiricism still rules development of therapy for AML. As a corollary, there is currently an emphasis on trials that enroll a relatively small number of patients, allowing more drugs to be tested (10, 11).

Our most recent effort in these patients involved tosedostat (an aminopeptidase inhibitor) combined with either ara-C or decitabine, as decided by randomization (protocol 2566). However a case of myocarditis in a patient given single agent tosedostat at another hospital prompted the FDA to interdict use of tosedostat in all studies. Nonetheless, although formal stopping criteria had not been met, it appeared unlikely that either arm of

our study would lead to a major improvement in survival (OS) or CR, although both arms had relatively little toxicity, allowing patients to spend the majority of their time as outpatients. Given that we have placed 3 patients on the tosedostat + decitabine or ara-C monthly for 12 months, that the length of the FDA hold is uncertain, and that the likelihood of major success with these combinations seemed small we have decided we need a replacement study.

While recognizing that there are many candidates for such a study, we have chosen a combination of decitabine and cytarabine. Reasons are as follows:

- a.) Data suggesting 10 days of decitabine produces higher response rates than the usual 5 days (12,13).
- b.) Decitabine followed by standard chemotherapy 7+3 appeared to be promising in a published phase I study (14). The rationale for decitabine in older patients is that there is abnormal DNA methylation in AML and hypomethylation agents have had efficacy in myelodysplastic syndrome, and to a lesser extent, AML. The theory is that hypomethylating agents may act by "priming" cells to susceptibility to subsequent chemotherapy. Toward the goal of studying this principle, our center currently has an ongoing trial of decitabine followed by MEC (mitoxantrone/etoposide/cytarabine) chemotherapy for relapsed patients (protocol 2652) (NCT01729845).
- c.) Although ara-C has yet to be combined with 10 days of decitabine, the absence of toxicity with tosedostat + much higher doses of ara-C than proposed here (1 g/m2 vs. 0.1 g/m2) suggests excess toxicity will not be an issue given that the patients to be treated are very similar to those treated in the tosedostat trial; in any event stopping rules are in place for short survival.
- d.) Two studies were presented in abstract form describing combinations of concurrent decitabine and cytarabine administration in patients. One pilot study combined decitabine 20 mg/m²/day X 5 days and cytarabine 20 mg/m²/day X 5 days with G-CSF priming in patients with MDS or AML (NCT00740181) (15). Grade 3 and 4 toxicities included mucositis and pulmonary infiltrates/infection. One of 5 patients achieved CR, two had progressive disease, and 2 were not evaluable. The other study combined ara-C and decitabine at higher doses than proposed here (150 mg/m²/dose for ara-C and 25-30 mg/m²/dose for decitabine) for 7 + 4 days (followed by SCT) with a higher CR rate and without increase in either severe infection rate or earlymortality over decitabine alone in MDS (NCT01674985) (16). There is a 3rd study listed on clinicaltrials.gov entitled "Phase II Study of Decitabine and Cytarabine for Older Patients with Newly Diagnosed Acute Myelogenous Leukemia (AML) (NCT01829503) that is open for enrollment.
- e.) There was a preclinical study in xenograft mice, where different schedules of decitabine and cytarabine were administered either concurrent or sequential, with no difference observed in the reduction of leukemia burden, although there were differences in methylation (17).
- f.) The absence of pharmaceutical company sponsorship will permit flexibility, thus allowing us to examine how physicians use data to decide on dose escalation. In particular, after receipt of 2 courses of therapy patients will be classified as being

in CR (<5% marrow blasts by morphology, neutrophil count > 1,000, platelet count > 100,000) or not. Patients not in CR will be further classified as having (a) <5% marrow blasts by morphology (but with counts not meeting the above criteria for CR), (b) \geq 20% marrow blasts by morphology, or (c) 5-19% marrow blasts by morphology. Patients in (a) will receive a 3rd cycle at the same doses and patients in (b) will receive an escalated dose of ara-C (1g/m2 daily days 1-5, as in the ara-C arm of the tosedostat study). For patients in group (c) physicians will decide whether to keep the ara-C dose at 0.1g/m2 daily days 1-7 or to escalate it to the 1g/m2 daily X 5 dose noted in (b) above. We will formally elicit the criteria used to arrive at this decision. These might include marrow cellularity, decrease in blasts or cellularity (or their product) compared to pre-treatment, toxicity (although dose escalation will not be allowed if grade ≥ 3 non-hematopoietic toxicity occurred on the first 2 courses), patient age or wishes etc. It is not apparent that the decision-making process for dose escalation has been investigated before. That this is a topic of interest however seems clear from our observations that while generally the higher the blast count the more likely that physicians are to begin a 2nd course within 1 week of a day 14 marrow there is considerable overlap with some patients with high marrow blast counts not receiving a 2nd course and vice versa and with the reasons for these decisions quite opaque (18).

g.) In turn the schema outlined in 3 will permit us to compare outcomes in patients in the intermediate (5-19% blast) group according to whether they received the same or an escalated dose on course 3. Of course the effect of a dose increase would likely be confounded by the effect of reasons the patient did or did not receive an escalated dose. However we will able to examine outcome on course 3 according to the reasons for giving/not giving an escalated dose.

3. Patient Eligibility

- a.) Newly-diagnosed AML by WHO criteria (≥ 20% myeloid blasts by morphology in either blood or marrow)
- b.) High-risk MDS or MPN including CMML2 as defined by 10-19 % myeloid blasts in either blood or marrow
- c.) Age ≥ 60
- d.) Patients may have received azacitidine, decitabine, or lenalidomide but no "cytotoxic therapy" such as ara-C or anthracyclines. Data suggest that failure to respond to azacitidine reduces probability of response to 3+7(19). Hence in the interest of having a relatively homogeneous population, while patients who have received and failed azacitidine or decitabine will be eligible for this study, they will be analyzed separately from patients who have not received these drugs.
- e.) Treatment related mortality (TRM) score < 22.9 (18). Patients with TRM scores > 13.1, in whom the risk of death within 28 days of beginning induction therapy has averaged 41%, will preferentially be placed on protocol 2642.
- f.) Provision of written informed consent
- g.) Note, unlike pharmaceutical company sponsored protocols eligibility is not conditioned on bilirubin, creatinine, or absence of other malignancy within the past 2-3 years. The TRM score incorporates creatinine and thus a high creatinine

can in principle be offset by favorable values for the other covariates in the TRM score (20). Bilirubin was not a covariate in the TRM. Furthermore, in the doses we are using, dose adjustment of decitabine or ara-C is not indicated in the presence of renal or hepatic abnormalities. Our broad eligibility criteria may increase the likelihood that our results will be generalizable. The inability to reproduce results of early phase AML studies has been a problem in the past (21).

4. Pre-treatment Evaluation

The following is a recommendation and will be collected from standard of care evaluations; missing items will not be considered a protocol deviation.

- a.) CBC, differential, platelet count
- b.) Chemistry to include bilirubin, ALT, AST, albumin, BUN, creatinine, electrolytes including calcium and magnesium
- c.) If not done within the previous 30 days bone marrow for morphology, flow, cytogenetics, FISH, and, with insurance approval, ONCOPLEX

5. Treatment Plan

The following is a recommendation and will be collected from standard of care evaluations; variations to the schedule will be done with physician discretion and will not be considered a protocol deviation.

- a.) Decitabine 20 mg/m2 daily IV days 1 through 10
- b.) Ara-C 100 mg/m2 once daily by IV bolus days 1 through 7
- c.) Patients will receive 2 such courses given 28-35 days apart regardless of blood counts.
- d.) On course 1 hydroxyurea will be given if the blast count (WBC X % blasts) either remains > 50,000 for 3 days after beginning decitabine+ ara-C or reaches this level after therapy is begun. Patients will be removed from study if hydroxyurea is still required more than 3 weeks after therapy is begun
- e.) Bone marrow will be examined 4-5 weeks after initiation of course 2, with decisions based on the result of this marrow and on assessment of non-hematologic toxicity on courses 1 and 2.
- f.) Patients will be re-evaluated after any 3rd course

Marrow response after course 2	Non hematologic toxicity	Plan
< 5% blasts (flow)	< grade 3	Course3 at same doses (dec 20 mg/m2 days 1-10, ara-C 100 mg/m2 days 1-7)
>19% blasts (flow)	< grade 3	Course 3 at same dose decitabine, but ara-C at 1 g/m2 daily X5 (days 1-5)

9019

7017		
5-19% blasts	<grade3< th="">Doctor decides	</grade3<>	Doctor decides
(flow)		between the 2 ara-
		C doses; reasons for
		decision elicited

<5% blasts	>grade 2	Course 3 at same
(flow)		doses as courses 1
		and 2, but duration
		shortened to
		decitabine days 1-8
		and ara-C days 1-5.
>4% blasts	>grade2	Off study
(flow)		

Response after course 3	Non hematologic toxicity	Plan
CR, CRp, CRi	< grade 3	1-2 more courses at same dose as course 3
	>grade 2	1-2 more courses at 20-50 % dose decreases
None of above	N/A	Off study

CR = < 5% marrow blasts (by morphology), ANC > 1000, platelet count > 100,000

CRp = as for CR but with platelet count < 100,000

CRi = <5% marrow blasts by morphology and either (a) marrow cellularity $\ge 15\%$, (b) at least 200 cells counted, or (c) ANC 500-1,000

6.) Post-treatment Testing

The following is a recommendation and will be collected form standard of care evaluations; missing items will not be considered a protocol deviation.

- a.) CBC, differential, platelets at least twice weekly
- b.) Electrolytes, BUN, creatinine at least weekly
- c.) Bone marrow exam after 2 cycles of therapy, as described above
- d.) If patient has 5-19% blasts by flow note reasons for decision to keep ara-C dose as on courses 1-2 or to increase it (see from below)

7.) Criteria For Removal From Study

- a.) Requirement for hydroxyurea to keep WBC < 50,000 more than 3 weeks after beginning treatment (see E4. above)
- b.) > grade 2 non-hematologic toxicity and > 4% blasts (by flow) after course 2
- c.) No CR, CRp, CRi after course 3
- d.) Physician's or patient's decision

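### The safety argument in Rationale 2.c and 2.d covers the 0.1 g/m2 ara-C starting dose but not the escalated course 3 (1 g/m2 x 5 with 10-day decitabine), and nothing in the plan reviews those courses as a group

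*Combined protocol and SAP*

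**What the plan says.** Section 2.c acknowledges that the combination is new ("Although ara-C has yet to be combined with 10 days of decitabine"). It then reasons that tosedostat given with "much higher doses of ara-C than proposed here (1 g/m2 vs. 0.1 g/m2) suggests excess toxicity will not be an issue", and adds that "in any event stopping rules are in place for short survival". Section 2.d cites two concurrent decitabine and ara-C studies, one at ara-C 20 mg/m2 and one at 150 mg/m2 per dose. Of the second it says "The other study combined ara-C and decitabine at higher doses than proposed here".

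The escalation is disclosed in 2.f: "patients in (b) will receive an escalated dose of ara-C (1g/m2 daily days 1-5, as in the ara-C arm of the tosedostat study". The section 5 table repeats it for more than 19% blasts with toxicity below grade 3: "Course 3 at same dose decitabine, but ara-C at 1 g/m2 daily X5 (days 1-5". At 5-19% blasts the physician chooses between the two ara-C doses. Below 5% the ara-C dose stays at 100 mg/m2. A gate applies: "dose escalation will not be allowed if grade ≥ 3 non-hematopoietic toxicity occurred on the first 2 courses". Patients who respond after course 3 may have one or two more courses at the course 3 dose, or at a 20-50% reduction after toxicity above grade 2.

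The precedent for 1 g/m2 is protocol 2566, described in section 2 as tosedostat "combined with either ara-C or decitabine, as decided by randomization". The survival rule in 8.c stops the trial at 5 or fewer of 10, or 12 or fewer of 20, alive at 6 months, counting all patients.

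**The concern.** Both safety comparisons use 0.1 g/m2 as the proposed dose, but some patients will receive ten times that per day. For them the margin in 2.c disappears, and the dose called higher in 2.d is well below what they get. Because protocol 2566 gave ara-C or decitabine and not both, its tolerability does not carry over to the pair.

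What 2.c then falls back on is a survival count over all patients. Escalated patients are aged 60 or over with persistent blasts after two courses. If their course 3 were unusually toxic, the pooled count would register only deaths. It would do so months later, mixed with deaths from resistant leukemia. Non-fatal toxicity would be handled patient by patient, with no planned look at the 1 g/m2 courses together.

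**Working it through.** **Dose.** Inputs are from section 5 and 2.d.

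| Comparison | Per dose | Per course |
|---|---|---|
| Course 3 escalated vs courses 1-2 | 1000/100 = 10 | 5 x 1000 / (7 x 100) = 7.1 |
| Course 3 escalated vs highest concurrent dose cited | 1000/150 = 6.7 | 5 x 1000 / (7 x 150) = 4.8 |

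The 4.8 reads the cited 7 + 4 schedule as seven ara-C days, which is an assumption.

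**The plan's own table.** I used exact binomials at 10, 20 and 30 patients with OS6 and complete remission (CR) independent. The trial stops at OS6 <= 5/10 or <= 12/20, or CR <= 1/10 or <= 4/20, and is positive at OS6 >= 20/30 and CR >= 8/30. At OS6 80%, CR 45%, this gives 8.6% early stopping and 90.0% positive (plan: 9% and 90%). At 65%, 45% it gives 46.5% and 41.0% (plan: 47% and 41%). At 50%, 45% it gives 88.8% and 3.6% (plan: 89% and 4%). All five rows agree within 2 points. The 89% applies only if OS6 falls to 50% in the whole cohort.

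**Dilution.** The share escalated is not in the documents, so I assume 20-40%, with OS6 80% in the rest and CR 45%. Pooled OS6 = (1 - f) x 0.80 + f x q.
- Escalated OS6 q = 50%: pooled OS6 74% to 68%, early stopping 19% to 36%.
- q = 30%: pooled OS6 70% to 60%, early stopping 30% to 64%.

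**Bounding case, OS6 rule alone.** Suppose exactly k of each 10 patients are escalated and all die by 6 months from any cause. Then the number alive per 10 is Bin(10 - k, p).

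| k per 10 | p = 0.80: at 10 / by 20 | p = 0.65: at 10 / by 20 |
|---|---|---|
| 0 | 3% / 5% | 25% / 45% |
| 1 | 9% / 16% | 39% / 67% |
| 2 | 20% / 43% | 57% / 88% |
| 3 | 42% / 80% | 77% / 98% |

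At p = 0.65 the rule already stops 45% of trials with no added deaths in course 3. At k = 2, p = 0.80, overall OS6 is 8 x 0.80/10 = 64%, so the 43% is close to the 47% the plan discloses at its null. The rule responds to overall survival, as intended, and does not indicate where the deaths come from.

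**Timing.** Course 3 starts at day 28 + 28 = 56 to 35 + 35 = 70. A 28-day window closes at day 84-98, which is 85-99 days before that patient's 6-month point (day 183). At 30 patients a year (2.5 a month) the tenth enrols at about month 4, and the first OS6 count is complete at about month 10. By then every escalated course 3 in that cohort has begun.

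**Proposed trigger: 2 deaths in the first 6 escalated.** P(at least 2) = 1 - (1 - q)^n - n q (1 - q)^(n - 1).

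| 28-day death rate q (assumed) | n = 6 | n = 3 |
|---|---|---|
| 6% | 4.6% | 1.0% |
| 12% | 15.6% | 4.0% |
| 30% | 58.0% | 21.6% |
| 40% | 76.7% | 35.2% |

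The 6% is the appendix figure for scores below 22.81 at first induction, so it may be too low for a third course in refractory disease. Only the first 1 g/m2 course should count: over three courses at 6% each, the per-patient risk is 1 - 0.94^3 = 16.9%, and the false-pause rate with n = 6 rises to 27%.

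**Patients spared at q = 30%.** If the second death is the t-th escalated patient (t up to 6), its probability is (t - 1) x 0.3^2 x 0.7^(t - 2), and N - t later patients are spared. Assuming instant detection and a pause that is not lifted, the expected number spared is 0.1 of N = 3, 1.1 of 6 and 2.9 of 9.

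**The case against.** The best defence is that 8.a tests the combination as given in section 5, and section 5 includes the escalation. Pooled OS6 is then the correct endpoint. A reader might infer that the rule would wrongly close a sound 0.1 g/m2 regimen for the faults of a higher dose, but the protocol does not treat the starting dose as a separate regimen. This stands.

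A reader might also infer that the escalation is hidden or that 2.c and 2.d are false. Neither is supported. Both sections are true of the starting dose, and 2.f states the escalation and its source. Section 2 reports little toxicity in both arms of protocol 2566, and 2.c describes its patients as very similar. The argument is incomplete rather than wrong.

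Safeguards for the individual are real: the grade 3 gate, physician discretion over the schedule (opening of section 5), removal by physician or patient (7.d), dose cuts after course 3, accrual holds, frequent investigator review, and committee review including the DSMC. They act on single patients or on the trial as a whole. None sets a look at the 1 g/m2 courses together.

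The bounding case is rightly criticised. Section 2 attributes most failures to resistance, so deaths in patients with persistent blasts cannot be read as ara-C toxicity. Fixing k per 10 is also artificial: if the number escalated varies at random, the first-look figures at p = 0.80 become 12%, 27% and 47%. The table shows what the pooled rule can distinguish, and it does not estimate harm.

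Finally, the trigger is weak when few are escalated, and cause of death is hard to assign in refractory disease. Both points stand and limit what the fix can promise.

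**Conclusion.** The point holds in a limited form. The cited evidence supports the 0.1 g/m2 starting dose and, separately, ara-C at 1 g/m2. It does not support 1 g/m2 x 5 together with 10-day decitabine, which exceeds the highest concurrent ara-C dose cited by 6.7-fold per dose and about 4.8-fold per course. The survival rule named as the fallback suits the overall strategy but is late and cannot separate toxicity of escalation from resistance.

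A stronger inference, that the escalated course is unsafe or unprotected, is not supported: the documents contain no toxicity data on the pairing, and several safeguards apply to each patient. The probabilities rest on an assumed number escalated and assumed death rates. The dose ratios and timing come from the protocol, apart from the reading of the 7 + 4 schedule. This is a cheap improvement and does not challenge the design or the primary endpoint.

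**What to change.** 1. Tabulate grade 3 or higher non-hematologic toxicity, and deaths within 28 days of course start, separately for 1 g/m2 and 0.1 g/m2 courses. Send the table to the DSMC at the 10- and 20-patient holds.
2. Add to 8.c a trigger for escalation only. If 2 of the first 6 escalated patients die within 28 days of starting their first 1 g/m2 course, without documented progression as the cause, no new 1 g/m2 course starts until the DSMC has reviewed. Accrual and the 0.1 g/m2 regimen continue.
3. State the limits beside the trigger: detection at 30% mortality is 58% with 6 escalated and 22% with 3; false pause with 6 is 5-16% at assumed rates of 6-12%; attribution of death is imperfect in refractory disease. With few escalated, the table in item 1 carries most of the weight.

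The cost is one table split by dose and one rule. Dose, dates, survival and grade 3 or higher events are already needed, so only a cause-of-death field is new. The downside is a possible temporary loss of escalated patients for objective 1.d. Rewording 2.c and 2.d alone would protect no one.

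### The rules for course-3 dosing, recording of reasons and removal band blasts by flow without excluding CR, while objective (c) and 2.f define the dose-choice group as not in CR, by morphology

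*Combined protocol and SAP*

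**What the plan says.** **Who the dose-choice group is meant to be.** Objective (c) in section 1 concerns an intermediate response "short of CR to the first 2 cycles of the combination". Section 2.f first separates patients in CR and then bands only the others: "Patients not in CR will be further classified as having (a) <5% marrow blasts by morphology". The group in which the physician chooses the ara-C dose is "c) 5-19% marrow blasts by morphology". Section 2.g then proposes to "compare outcomes in patients in the intermediate (5-19% blast) group according to whether they received the same or an escalated dose" and names no assay.

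**How the group is operated.** Section 5.e says "Bone marrow will be examined 4-5 weeks after initiation of course 2, with decisions based on the result of this marrow". In the table that follows, all five course-2 rows give blasts by flow, crossed with non-hematologic toxicity. None mentions CR or blood counts. Item 6.d asks for the physician's reasons in the same flow band: "If patient has 5-19% blasts by flow note reasons for decision to keep ara-C dose as on courses 1-2 or to increase it". Item 7.b removes patients who have more than 4% blasts by flow after course 2 and toxicity above grade 2.

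**How CR is defined.** Section 5 gives "CR = < 5% marrow blasts (by morphology), ANC > 1000, platelet count > 100,000", with no flow criterion. After course 3 the plan turns on CR, CRp or CRi, so on morphology. A responder with toxicity above grade 2 then gets "1-2 more courses at 20-50 % dose decreases".

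**The concern.** The stated population and the operating rules use different assays, and only the stated population excludes CR. No text reconciles the two or says which prevails.

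Three things are at stake:

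- **Treatment.** A patient in CR may have ara-C escalated, or lose further study treatment, because of a flow result that plays no part in the definition of CR.
- **Data for objective (c).** Reasons are requested from some patients outside the objective and not from some inside it.
- **Consistency between sites and physicians.** Someone working from 2.f and someone working from the table can reach different course-3 plans for the same marrow.

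**Working it through.** The plan gives no figure on this point, so the check sets the rules side by side.

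**1. Assay and CR condition by location**

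| Location | Assay for blasts | CR excluded? |
|---|---|---|
| Objective (c) | not named | yes |
| 2.f bands | morphology | yes |
| 2.g comparison | not named; follows 2.f | by reference to 2.f |
| Section 5, five course-2 rows | flow | no |
| 6.d | flow | no |
| 7.b | flow | no |
| CR definition, section 5 | morphology plus counts | – |

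**2. A patient in CR.** Take illustrative values of 3% blasts by morphology, 7% by flow and recovered counts. This patient is in CR and has no band under 2.f. For any patient in CR, the five course-2 rows give:

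- flow <5%, toxicity <grade 3: same doses
- flow 5-19%, toxicity <grade 3: physician chooses the ara-C dose, and 6.d applies
- flow >19%, toxicity <grade 3: ara-C escalated
- flow <5%, toxicity >grade 2: shortened course
- flow >4%, toxicity >grade 2: off study, as in 7.b

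Three of the five rows lead to optional escalation, required escalation or removal. The example patient falls in the second row or the fifth, depending on toxicity.

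**3. The opposite case.** A patient with 5-19% by morphology, <5% by flow and toxicity <grade 3 is in the 2.f dose-choice group. The table assigns the same doses as before, and 6.d does not ask for reasons.

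**4. All combinations for patients not in CR, toxicity <grade 3.** Crossing three morphology bands with three flow bands gives 9 combinations.

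- In 3 of them, 2.f and the table agree.
- In 4, one rule fixes the dose and the other leaves it to the physician.
- In 2 (<5% by one assay, 20% or more by the other), the rules require different doses.
- Group membership: 3 combinations by flow, 3 by morphology, 1 shared, so 3 + 3 − 1 = 5 by either rule and 1 by both.

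These are combinations of rules and say nothing about how often each occurs.

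**5. Size of the dose difference.** Standard ara-C is 100 mg/m2 × 7 days = 700 mg/m2 per course. Escalated ara-C is 1,000 mg/m2 × 5 days = 5,000 mg/m2. The ratio is 5,000 / 700 = 7.1.

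**6. Does this reach the primary decision rules?** An exact three-look binomial calculation took OS6 and CR as independent and read the CR stopping limits as ≤1/10 and ≤4/20. It reproduces the section 8.d probabilities of a positive trial:

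| OS6 / CR | Computed | Stated |
|---|---|---|
| 80% / 45% | 90.0% | 90% |
| 80% / 60% | 93.6% | 94% |
| 65% / 25% | 17.3% | 17% |
| 65% / 45% | 41.0% | 41% |
| 50% / 45% | 3.6% | 4% |

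The inputs are counts of patients alive at 6 months and counts of CR. Neither the flow bands nor the course-3 dose enters these rules.

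**The case against.** **The analysis group is better defined than the table suggests.** A reader might infer that objective (d) has no fixed population, or that patients already in CR will contaminate the comparison. The documents do not support that. Section 2.g directly follows 2.f, and the only intermediate group defined by then is the 2.f group: not in CR, 5-19% by morphology. Objective (d) refers back to the escalation described in objective (c). Section 2.f also has every patient classified as in CR or not after course 2, so patients in CR can be excluded at analysis. This objection stands for (d). It does not settle course-3 dosing, removal or which patients have reasons recorded.

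**Flow may be deliberate.** It is used consistently in all five rows, 6.d and 7.b, while the morphology bands appear only in the Rationale. Dosing by flow while defining CR by morphology is not an error in itself, and the choice is partly clinical. Nor is it a contradiction for the rules after courses 2 and 3 to differ. This stands too. If flow is intended, however, 2.f is wrong and the handling of a patient in CR is still unstated.

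**The rules are soft.** Sections 5 and 6 are prefaced as recommendations, and 7.d already allows removal by physician or patient decision. That eases enforcement but does not say which assay defines the group, and neither preface covers 7.b.

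**Some text may be missing.** Item 6.d points to something below, apparently a form, that is not in the text available. Whether it limits collection to patients not in CR cannot be judged.

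**Conclusion.** The mismatch is real. The stated dose-choice group and the rules that operate it differ in assay and in whether CR is excluded. Following the rules literally can escalate or remove a patient in CR, and it misses the reasons for some patients inside objective (c). The main harm is to course-3 treatment, removal and data collection for (c).

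Its size in patients cannot be computed, because the documents give no rate of disagreement between morphology and flow. A reader might take the counts of rows and combinations above as a frequency. They are not one: they weight all combinations equally, and nothing in the documents shows that the extreme ones (<5% by one assay, 20% or more by the other) occur.

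The OS6 and CR decision rules are unaffected. Objectives (c) and (d) are descriptive, have no sample size or decision rule, and concern a subset of at most 30 patients. Severity is minor: worth correcting at the next amendment. The conclusion rests on a literal reading of the table, 6.d and 7.b.

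**What to change.** Make one amendment with these parts:

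1. Name one assay for the blast bands and use it in 2.f, the five course-2 rows, 6.d and 7.b. Morphology matches the CR definition. If flow is intended for dosing, change the 2.f bands to flow.
2. Add *and not in CR* to the 5-19%, >19% and >4% rows, to 6.d and to 7.b. Add *or in CR* to the two <5% rows, so that patients in CR still have a plan. With morphology these words are redundant but harmless; with flow they are essential.
3. State in 2.g that the analysis group for (c) and (d) is this same group.
4. Record the other assay's percentage on the reasons form.

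**Cost.** No new procedure is needed: the table already requires flow on the course-2 marrow, and CR requires morphology. A few patients with discordant assays would change plan:

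- Under morphology, patients with <5% by morphology and 5% or more by flow lose the escalation option, and some 7.b removals change in each direction.
- Under flow with the CR condition, only patients in CR change plan relative to the current table. Patients with 5-19% by morphology but <5% by flow stay outside the dose-choice group.

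Patients already dosed by flow stay as treated and are flagged in the analyses for (c) and (d).
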